5.3 Concomitant Interventions

Required medications: Inhaled corticosteroids with or without long-acting beta agonists.

Allowed medications: Long acting anti-muscarinics, montelukast, or other medications not specifically excluded.

Prohibited medications: anti-coagulants such as warfarin, rivaroxaban and similar agents

5.3.1 Allowed Interventions

Subjects will continue their usual asthma medications during the study except for the washout periods listed in section 4.1. Patients will continue their inhaled corticosteroids with or without inhaled long acting beta agonists and/or long acting anti-muscarinic medications. Additional asthma medications (e.g. montelukast) are also allowed. Rescue of asthma symptoms with short-acting beta agonists is also allowed and if this occurs within a washout period, the study visit will be re-scheduled. Subjects who are not excluded due to the use of anti-coagulants will continue the use of all other prescribed medications.

5.3.2 Required Interventions

No other required interventions.

5.3.3 Prohibited Interventions

Subjects prescribed anti-coagulants (warfarin, rivaroxaban and similar agents) are excluded from participating in the study and are prohibited while the participant is in the study.

5.4 Adherence Assessment

Adherence will be recorded by pill counts at the 28 day and 56 day visit. Adherence will be defined by at least 70% of the capsules consumed. Compliance will be calculated as such:

Number of doses taken by the subject = Number of pills dispensed – number of pills returned

Number of doses expected = will be calculated by the SC based on the date of visit and original date dispensed, times the number of pills that should be taken per day

$$\text{Adherence} = 100 - \left(\left(\frac{\text{Number of doses expected} - \text{number of doses taken by the subject}}{\text{number of doses expected}} \right) * 100 \right)$$

6. STUDY PROCEDURES

6.1 Schedule of Evaluations

Assessment	Screening: Visit 1 (Day 1)	Baseline, Enrollment Visit 2 (Day 14-21)	Study & Randomization Visit 3 (Day 15-22)	Study Visit Visit 4 (Day 43-50)	Study Visit Visit 5 (Day 71-78)
Informed Consent Form	X				
Demographics	X				
Administer Asthma Control Test (ACT)	X	X	X	X	X
Administer QOL questionnaire			X	X	X
Administer 2 week recall questionnaire			X	X	X
Confirm Medication Washouts	X	X	X	X	X
Medical History	X		X		
General Physical Examination	X		X	X	X
Urine pregnancy test for women of childbearing age	X		X	X	X
Inclusion/Exclusion Criteria	X		X		
Vital Signs	X		X	X	X
Spirometry	X	X	X	X	X
Post-Bronchodilator Spirometry	X				
Methacholine Bronchoprovocation		X		X	X
Administer bronchodilator	X	X		X	X
Methacholine Recovery challenge		X		X	X
GI side effects checklist			X	X	X
Measure exhaled nitric oxide			X	X	X
Blood draw for cytokines, eosinophilia, biomarkers			X	X	X
Enrollment/Randomization			X		
Pre-dose blood draw for PK subjects			X	X	X
Administer dose of study drug			X	X	X
Post dose spirometry (1hr)			X		
PK blood draws for selected subjects			X	X	X
Dispense drug			X	X	
IP Accountability				X	X
Concomitant Medications	X	X	X	X	X
Adverse Events	X	X	X	X	X

6.2 Description of Evaluations

Informed Consent Form: If the potential enrollees are interested in participating, they will meet with the study Coordinator and local physician co-investigators to review the study and to ask questions. They will be asked to sign consent. A copy of the consent form will be given to each participant, and the signed original will be kept in the participant's research chart. Only participants who are capable of providing their own informed consent will be enrolled. The consents, HIPAA Authorization and all study questionnaires will be available in English and Spanish.

Demographics: Collection will include age, gender, race, education and zip code.

Asthma Control Test (ACT): Asthma symptom score will be measured with the Asthma Control Test at all visits. This instrument, which has been validated for ages 12-84 years, is a 5 question, 4-week recall questionnaire that addresses issues of asthma control, symptoms, and nocturnal awakenings.

Juniper mini-Asthma specific quality of life (QOL): Asthma specific quality of life is measured with instruments developed and validated by Juniper, Guyatt and colleagues.

Asthma Two Week Recall: The Asthma two week recall (A2WR) was developed to capture the inherent intensity of the disease in individuals with asthma. It quantifies severity by combining information about impairment, risk, and the amount of medication required to maintain control.

Confirm Medication Washouts: Cessation of medications will be confirmed at study visits as described in the table in section 4.1. If inadequate washouts have not occurred, the study visit will be re-scheduled.

Medical History: Relevant medical history, including history of current disease, other pertinent respiratory history, and information regarding underlying diseases will be recorded at the Screening visit and confirmed during the randomization visit.

General Physical Exam: A complete physical examination will be performed by either the Investigator or a Sub-Investigator as indicated on the Schedule of Events. Complete physical examinations will include a minimum of a review of the subject's general appearance, head, eyes, ears, nose, and throat (HEENT), neck, heart, lungs, abdomen, extremities, skin, and general neurological system. Symptom-oriented or brief physical examinations will be performed at time points noted in the Schedule of Events and as clinically indicated. New abnormal physical exam findings not present during the follow up visits will be recorded as AEs and followed during subsequent visits.

Concurrent Medications/therapies: Will be documented throughout the course of the study. Dose, route, unit frequency of administration, and indication for administration and dates of medication will be captured.

Urine Pregnancy Test: A urine pregnancy test will be obtained from female subjects who are of childbearing age prior to their participation and at every study visit in this study.

Inclusion/Exclusion Criteria:

Inclusion Criteria:

Subjects must meet all of the inclusion criteria to participate in this study.

1. Adults aged 18 years and above, with mild to severe persistent asthma will be enrolled as defined by The NIH National Asthma Education and Prevention Program (NAEPP) Guidelines for Assessing Asthma Severity¹ (please see table page 9). Subjects will have asthma which is not optimally controlled as defined by Asthma Control Test (ACT) score, despite the current use of inhaled corticosteroids with or without inhaled long-acting beta agonists.
2. Treatment with inhaled corticosteroids (ICS) +/- long acting β -agonists/long acting muscarinics and montelukast;

3. Physician diagnosed asthma, confirmed by patient history/report, as well as pulmonary function test (FEV1 \geq 60% of predicted or 1.5 L) and methacholine testing (Baseline methacholine PD20 < 16 mg/ml if taking ICS or < 8 mg/ml if not taking ICS at Visit 2) to confirm diagnosis.
4. Non-smoker (e.g., tobacco, e-cigarette, marijuana) for \geq 1 yr.; Nicotine patch or gum is allowed.
5. \leq 10 pack-year smoking history;
6. Suboptimal control of asthma as determined by a score < 19 or less on the Asthma Control Test (ACT) at Screening and Randomization Visits.
7. Ability to understand the English or Spanish language and to understand the study procedures and comply with them for the entire study period.
8. Females of childbearing potential: Pregnant or lactating; participants of appropriate age will be screened with urine pregnancy tests at each visit and cannot participate if pregnant. Participants must agree to use effective contraception during the trial.

Exclusion Criteria:

Subjects with any of the exclusion criteria will be excluded from study participation.

1. Other major chronic illnesses: Conditions which in the judgment of the study physician would interfere with participation in the study, e.g., non-skin cancer, uncontrolled diabetes mellitus, coronary artery disease, congestive heart failure, stroke, severe hypertension, renal failure, liver disorders, malabsorption disorders, immunodeficiency states, major neuropsychiatric disorder;
2. Cardiovascular problems:
 - a. Myocardial infarction or stroke in last 3 months
 - b. Uncontrolled hypertension
 - c. Known aortic aneurysm
3. History of physician diagnosis of chronic bronchitis, emphysema or COPD
4. Medication use:
 - d. Current consumption of ginger supplements
 - e. oral corticosteroid use within the past 6 weeks
 - f. use of an investigational treatment in the previous 30 days
 - g. Use of anti-coagulation such as warfarin, rivaroxaban and similar agents.
5. Known adverse reaction to ginger or ginger products
6. Subjects with cancer, other than skin cancer, will be excluded.
7. Current drug or alcohol use or dependence that, in the opinion of the site investigator, would interfere with adherence to study requirements
8. Inability or unwillingness of individual or legal guardian/representative to give written informed consent.

Vital Signs: Height, weight, smoking status, number of pack years will be collected at the screening visit. Measurement of body temperature, blood pressure, pulse, SpO2 and respirations will be performed after resting for 5 minutes at every visit.

Spirometry: Subjects will be asked to perform pulmonary function testing for collection of lung function data at each visit. Pulmonary function testing will be performed according to American Thoracic Society (ATS) guidelines (2005). Subjects will be tested using the same spirometry equipment at every visit. Up to 8 efforts will be performed to obtain 3 acceptable and reproducible test results. The best results from the 3 acceptable and reproducible efforts for PFTs will be recorded on the subject's case report form and a copy of the spirometry reports will be retained with the subject's source documents.

Post-Bronchodilator Spirometry: Will be performed 15 mins after inhalation of 4 puffs of a short acting Bronchodilator.

Methacholine Provocation: A methacholine challenge test is a medical test used to assist in the diagnosis of asthma. The patient breathes in nebulized methacholine at gradually increasing doubling doses, starting with diluent only. Methacholine provokes bronchoconstriction, or narrowing of the airways via M3 receptors. The degree of narrowing can then be quantified by spirometry which is performed after inhalation of each dose. Once the FEV1 drops by 20% or more from baseline diluent spirometry, the test is halted.

Methacholine Recovery Challenge Albuterol will be administered by inhalation (4 puffs) at the end of the methacholine provocation test to return the patients FEV1 back to baseline:

GI side effect checklist: Patients will be asked about the frequency and severity of GI symptoms including eructation, heartburn, nausea, bloating or indigestion at Visits 3,4 and 5.

Measured Exhaled Nitric Oxide (FeNO): FeNO is widely used as a global measure of lung inflammation. Exhaled breath will be collected from forced expirations using disposable mouthpieces for the online exhaled NO (Circassia) procedure described in the American Thoracic Society (ATS) guidelines. FeNO levels will be measured at Visits 3,4 and 5.

Blood Draw for Cytokines, eosinophilia, biomarkers: Peripheral venous blood will be collected at Visit 3, 4 and 5 for the measurement eosinophils and cytokines and biomarkers. 8 subjects will also have blood collected for pharmacokinetic studies. Eosinophils counts will be measured in the Center for Advanced Laboratory Medicine (CALM) lab in the Department of Pathology at Columbia University located at [name]. Multiplex cytokine analyses will be performed in the laboratory of [name], Department of Anesthesiology, [name].

Enrollment/Randomization: Randomization to either ginger capsules or placebo will be done using a randomization algorithm within REDCap in a blinded fashion (group A or B).

Pre-Dose blood draw for PK subjects: Study drug should be withheld the day of the study visit for the PK subgroup. Study drug will be administered in the clinic after the pre-dose PK blood draw

Administer Study Drug: At the randomization visit, subjects will receive 2 capsules of either ginger extract (~500mg) or identical appearing placebo based on their randomization group.

Post-Dose Spirometry (1hr): On visit 3, Subjects will repeat spirometry 1 hr after the ingestion of 2 capsules of ginger extract (~500mg capsules) or two capsules of placebo to determine if there is an acute bronchodilatory benefit of ginger.

PK blood draws for PK subjects: Pharmacokinetic (PK) Measurements:

Subject plasma will be obtained for the measurement of PK measurements at Visit 3, Visit 4, and Visit 5 from a group of 8 subjects (4 Males & 4 Females). Serum samples will be collected at the following time points before and after the oral ingestion of 1g ginger; *At Day 1, 28 & 56:* Pre Dosing (time 0), Post Dosing 0.5, 1, 2,3, 4,& 8 hrs. We will quantify major metabolites of 6-shogaol (i.e. M2, M6, M9, and M11) and major metabolites of 6-gingerol (6-gingerdiols). Samples will be aliquoted and stored in such a manner that additional metabolites of these ginger components and additional ginger components (8-shogaol, 10-shogaol, 8-gingerol, 10-gingerol) and their metabolites can be evaluated in future studies. Samples will be processed, aliquoted and stored in the research laboratory of [name] ([name]. Plasma samples will be shipped on dry ice to the laboratory of [name] at [name].

Dispense Drug: Capsules containing ginger extract (~500mg) or placebo will be ingested by the patient at a recorded time at the randomization visit to allow for 1hr post-spirometry and PK measurements in selected subjects. Drug will also be dispensed at visit 4.

Pill Count: At study visits 4 and 5 pill counts will be recorded to document compliance with the study drug or placebo.

Concomitant Medications: All current medications will be recorded including dose and last time taken.

Adverse Events: Definition of adverse event/serious adverse event: An Adverse Event (AE) is any unfavorable and unintended symptom, or disease temporally associated with the administration of ginger or the clinical testing proposed that may or may not be considered related to the medical treatment or procedure.

Classification of adverse event severity: We will utilize the National Cancer Institute Common Toxicity Criteria (CTCAE) Grades 1 through 5 with unique clinical descriptions of severity for each AE based on this general guideline:

Grade 1 Mild; asymptomatic or mild symptoms; clinical or diagnostic observations only; intervention not indicated.

Grade 2 Moderate; minimal, local or noninvasive intervention indicated; limiting age-appropriate instrumental ADL.

Grade 3 Severe or medically significant but not immediately life-threatening; hospitalization or prolongation of hospitalization indicated; disabling; limiting self care ADL.

Grade 4 Life-threatening consequences; urgent intervention indicated.

Grade 5 Death related to AE.

Reporting of Serious Adverse Events A serious adverse event (SAE) is defined by federal regulation as any AE occurring at any dose that results in any of the following outcomes: death, life-threatening AE, hospitalization or prolongation of existing hospitalization, a persistent or significant disability/incapacity, or a congenital anomaly/birth defect. Serious adverse events occurring after signing the informed consent and during the follow-up period, including laboratory test abnormalities fulfilling the definition of SAE, whether or not considered related to the study medications or procedures, will be recorded on the Serious Adverse Event form and forwarded to the study PI as soon as possible. The PI or designee will forward the reports to appropriate authorities (DSM, FDA, NHLBI, Pharmaceutical supplier) according to the institutional guidelines. All adverse events will also be reported to the IRB according to the institutional AE reporting guidelines. Every attempt will be made to collect discharge summaries for each hospitalization to provide further details.

Collect Unused Study Drug: Unused drug will be collected and Visits 4 and 5; upon completion of the study, unused study drug will be collected and destroyed.

6.2.1 Screening Evaluation

Adults 18 and older, with physician diagnosed mild to severe persistent asthma will be screened. After reviewing and signing informed consent, subjects that fulfill inclusion and exclusion criteria will be invited to participate.

Consenting Procedure

Single informed consent describing screening and study procedures.

The study PI ([name]) or the research study coordinator ([name]) will conduct the consent process.

[name] is a professor of medicine and pulmonologist and director of the John Edsall-John Wood Asthma Center at Columbia University Medical Center. [name], B.S. has over 3 years of experience as a clinical research coordinator and has experience consenting and studying pulmonary

patients during clinical studies in the John Edsall-John Wood Asthma Center.

Any changes in the consent form will only occur after approval from the institutional IRB and the NCCIH.

Documentation of the consent process and consent forms will be retained in a research study binder.

Screening

Visit 1: Screening Visit

Sequence of events:

- Identify patients that are adults 18 and older with physician-diagnosed mild to severe persistent asthma
- Sign informed consent
- Fulfill inclusion and exclusion criteria
- Review of medical history
- Record Demographics
- Recording of medication use
- Physical exam including vital signs by study MD or NP
- Urine pregnancy test for women of child bearing age
- Scoring on ACT ≤ 19
- Scoring on basic spirometry before and after bronchodilator

Required to be eligible:

- Patients that are adults 18 and older with physician-diagnosed mild to severe persistent asthma
- Signing informed consent
- Fulfill inclusion and exclusion criteria
- Using inhaled corticosteroids with or without inhaled long acting beta agonists or anti-muscarinics.
- Scoring on ACT ≤ 19
- Negative urine pregnancy test for women of child bearing age

Screening must be completed 14-21 days prior to visit 2 during which the ACT score will be confirmed to be ≤ 19 , and the baseline FEV1 is $\geq 60\%$ of predicted (or 1.5L); Baseline methacholine PD20 will be determined at V2 as a subsequent eligibility criterion.

Visit 2; Day 14 to 21:

- Administer ACT. If ACT remains ≤ 19 , proceed . If ACT > 19 consistent with good asthma control, terminate from study.
- Confirm medication washouts (reschedule if not met).
- Spirometry
- methacholine bronchoprovocation testing if FEV1 is $\geq 60\%$ or 1.5L (reschedule or terminate if $< 60\%$ or 1.5L) to assess baseline methacholine PD20.
- Administer BD for Methacholine Recovery Challenge

6.2.2 Enrollment, Baseline, and/or Randomization

Enrollment

A single informed consent form will be used for screening and enrollment. The enrollment date will be defined as the date that all of the screening criteria are met and the individual agrees to participate.

The enrollment date will be recorded on the case report form and the allowable window from enrollment to randomization will be 15-22 days.

Baseline Assessments

- Baseline FEV1
- Baseline methacholine PD20
- Baseline ACT score

- Baseline QOL and Asthma 2 week recall questionnaires
- Baseline GI symptoms
- Baseline Exhaled Nitric Oxide
- Blood draw for eosinophils, cytokines, biomarkers
- Blood draw for metabolite measurements in subjects participating in PK study

Randomization

Randomization to initiation of study intervention will occur on the same day. Randomization will occur at visit 3 and will precede an intervention (i.e. starting of oral ginger or placebo).

Randomization is a process that assigns participants/subjects by chance (rather than by choice) into specific groups, typically for clinical research and clinical trials. An independent statistician will generate the randomization codes and allocations. The blinded study coordinator will retrieve the randomization allocation through RedCap. RedCap is an institutionally available automated system for randomization and the independent statistician will have direct oversight over the process. The blinded study team will not have access to the randomization codes. In this module, randomization model is defined as Drug A and Drug B in a 1:1 ratio. Drug A and Drug B may refer to placebo or active drug, however they are left coded as such to ensure blinding. The module creates a template allocation table, which the user uses to structure the randomization table to be imported. The module also monitors the overall allocation progress and assignment of randomized subjects to ensure balanced proportions of active drug and placebo. Only one site member will be allowed randomization privileges, but the site will confirm, and lock the specific data field to ensure that no data is altered after randomization. There is no stratification, and there are no variable block sizes..

6.2.3 Blinding

Ginger extract and placebo capsules have been pre-packaged and labeled with a code by the distributor (Atrium Innovations, Pure Encapsulations) and delivered to the research pharmacy at the Columbia University Medical Center. We do not anticipate any collected data offering evidence of a participant's assignment to a particular arm. All study data is collected objectively without an opportunity for the collected data to identify the study arm. For example, changes in methacholine PD20 and exhaled nitric oxide (primary outcomes) will vary over the course of the study in both ginger and placebo treated subjects. These variations will not be able to offer evidence of group membership and will only be informative after analysis in the aggregate.

The study PIs, [name], [name] are authorized to break the blind if there is a concern for subject safety, a serious adverse event or safety concerns raised by the DSMB. The PIs will contact the independent statistician who will be holding the codes. The PIs, Research Coordinator, study statistician(s), subjects and research pharmacy will be blinded. The research pharmacy will be notified as to randomization to drug A or B but will be unaware of which is ginger versus placebo.

6.2.4 Followup Visits

Visit 3 Day 15-22 RANDOMIZATION VISIT

Procedures Performed:

- Administer questionnaires (ACT, QOL, A2WR)
- Review medical history, conmeds, and AEs since the screening visit
- Confirm medication washouts (reschedule if not met)
- Vitals
- Urine Pregnancy Test (if applicable)
- Physical Exam
- Review Randomization Inclusion/Exclusion Criteria
- Baseline GI side effect check list
- Randomize
- Measure Exhale Nitric Oxide (FeNO)

- Pre-dose Spirometry
- Blood draw cytokines, biomarkers and blood eosinophil count
- Pre-dose Pharmacokinetic blood draw for select subjects
- Administer 1st dose of study drug
- Post-Dose Spirometry (1 hr post-study drug dosing)
- Pharmacokinetic blood draw for select subjects (n =8 4 Males & 4 Females) (Time 0.5, 1, 2, 3, 4 & 8 hrs)- **PK Subgroup only.**
- Dispense drug

Visit 3A Day 29-36: Phone contact to answer questions and encourage compliance.

Visit 4 Day 43-50 (Day 28 of study drug):

Procedures Performed:

- Administer questionnaires (ACT, QOL, A2WR)
- Review conmeds, and AEs since V3
- Review study drug compliance (pill count)
- Confirm medication washouts (reschedule if not met)
- GI side effect checklist
- Vitals
- Urine Pregnancy Test (if applicable)
- Physical Exam
- Exhale Nitric Oxide (FeNO)
- Spirometry
- Perform Methacholine Challenge --- reschedule visit if FEV1 is < 60% or 1.5L
- Administer bronchodilator
- Methacholine Recovery Challenge
- Blood draw cytokines, biomarkers and blood eosinophil count
- Pre-dose Pharmacokinetic blood draw--**PK subgroup only.**
- Study Drug Dosing
- Pharmacokinetic blood draw (Time 0.5, 1, 2, 3, 4 & 8 hrs)—**PK subgroup only.**

Visit 4A Day 44-70: Phone or email contact to answer questions and encourage compliance.

Visit 5 Day 71-78 (Day 56 of study drug)

Procedures Performed:

- Administer questionnaires (ACT, QOL, A2WR)
- Review conmeds, and AEs since the previous visit (V4)
- Review study drug compliance (pill count)
- Confirm medication washouts (reschedule if not met).
- GI side effect check list
- Vitals
- Urine Pregnancy Test (if applicable)
- Physical Exam
- Exhale Nitric Oxide (FeNO)
- Spirometry
- Perform Methacholine Challenge --- reschedule visit if FEV1 is < 60% or 1.5 L
- Administer bronchodilator
- Methacholine Recovery Challenge
- Collect Blood for cytokines, biomarkers and eosinophil count
- Pre-dose Pharmacokinetic blood draw--**PK subgroup only.**
- Study Drug Dosing for PK group only
- Pharmacokinetic blood draw (Time 0.5, 1, 2, 3, 4 & 8 hrs)—**PK subgroup only.**
- Collect unused study drug.

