Day 43-50/Visit 4: Subjects will be asked to withhold morning dose of the study drug the day of the study visit. Women of child bearing potential will have a negative urine pregnancy test confirmed. Subjects will be asked to complete an ACT to assess asthma control and a validated asthma quality of life questionnaire (Juniper mini AQLQ). FeNO will be measured using a Circassia Niox Vero machine with disposable filters. Basic spirometry will be performed, Methacholine test will be performed if subject meets safety criteria ($FEV_1 > 1.5L$ or 60% predicted). 10ml of blood will be collected for measurement of cytokines, biomarkers and blood eosinophil count. For those patients in PK group, an additional 35 ml of blood will be collected over an additional 7 times points (pre-dose, 0.5 hour, 1 hour, 2 hour, 3 hour, 4 hour, and 8 hour). Study drug will be administered in the clinic after the pre-dose PK blood draw.

Unused study medication will be collected and pill count will be recorded.

Day 71-78/Visit 5: Subjects will be asked to withhold morning dose of the study drug the day of the study visit. Women of child bearing potential will have a negative pregnancy test confirmed. Subjects will be asked to complete an ACT to assess asthma control and a validated asthma quality of life questionnaire (Juniper mini AQLQ). FeNO will be measured using a Circassia Niox Vero machine with disposable filters. Basic spirometry will be performed. Methacholine hyperresponsiveness will be measured if subject meets safety criteria ($FEV_1 > 1.5L$ or $>60\%$ predicted). 10ml of blood will be collected for measurement of cytokines, biomarkers and blood eosinophil count. For those patients in PK group, an additional 35 ml of blood will be collected over an additional 7 times points (pre-dose, 0.5 hour, 1 hour, 2 hour, 3 hour, 4 hour, and 8 hour). Unused study medication will be collected and pill count will be recorded. Study drug will be administered in the clinic after the pre-dose PK blood draw.

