6.2.5 Completion/Final Evaluation

Visit 5 Day 71-78 (Day 56 of study drug)

Procedures Performed:

- Administer questionnaires (ACT, QOL, A2WR)
- Review conmeds, and AEs since the previous visit (V4)
- Review study drug compliance (pill count)
- Confirm medication washouts (reschedule if not met).
- GI side effect check list
- Vitals
- Urine Pregnancy Test (if applicable)
- Physical Exam
- Exhale Nitric Oxide (FeNO)
- Spirometry
- Perform Methacholine Challenge --- reschedule visit if FEV₁ is < 60% or 1.5 L
- Administer bronchodilator
- Methacholine Recovery Challenge
- Collect Blood for cytokines, biomarkers and eosinophil count
- Pre-dose Pharmacokinetic blood draw--**PK subgroup only.**
- Study Drug Dosing
- Pharmacokinetic blood draw (Time 0.5, 1, 2, 3, 4 & 8 hrs)—**PK subgroup only.**
- Collect study drug.

Any subjects who discontinue the study early will be contacted to determine the reason why. These reasons will be documented in the study binder. If termination occurs to lack of tolerance or adverse events related to the study drug or procedures, protocols for reporting adverse events will be followed as outlined below.

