9. STATISTICAL CONSIDERATIONS

9.1 General Design Issues

We hypothesize that the oral consumption of Pure Encapsulation® ginger extract (2g/day by adult patients with moderate to severe asthma despite normal maintenance medications, will have an improvement in their tolerance to inhaled methacholine or a reduction in lung inflammation over the 56 day treatment period.

This is a randomized, double blind, placebo-controlled design. Patients will have baseline measurements of their pulmonary function and inflammation status and will then be randomized to ginger extract or placebo. The same measurements of pulmonary function and inflammation status will be repeated at 28 and 56 days of ginger or placebo consumption. The durations of 28 and 56 days were chosen because it is hypothesized that the primary benefit of consumption of oral ginger will be an anti-inflammatory effect in

the lung that over time results in improved pulmonary function.

Primary hypotheses: are that the oral daily consumption of ginger will improve the tolerance to inhaled methacholine and/or a reduction in exhaled nitric oxide.

Secondary hypotheses: are that an additional measure of pulmonary function will improve (an increase in baseline FEV1) and/or that secondary measures of inflammation (eosinophilia, asthma associated cytokines) will improve.

Primary outcome measures: The primary outcome measures are methacholine (PD20) and exhaled nitric oxide. These outcomes will be measured at visit 3 (baseline) and visits 4 and 5 (days 28 and 56 of the oral ginger or placebo consumption).

Secondary outcome measures: A clinically significant increase in baseline FEV1 of 100ml. For subjects with eosinophilia (>300 cells/ul) a 32% decrease in blood eosinophils¹⁷, a 40% decrease in serum IL4^{18,19}, a 50% decrease in serum IL5²⁰ or a 75% decrease in serum IL13.²¹

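### At Visits 4 and 5 the eosinophil and cytokine blood draw is listed after the methacholine challenge and bronchodilator, but the Visit 3 baseline draw has neither that day; the draw should be placed before the challenge

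*Combined protocol and SAP*

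**What the plan says.** **Visit 3 (section 6.2.4).** The baseline draw, "Blood draw cytokines, biomarkers and blood eosinophil count", comes after exhaled nitric oxide (FeNO) and pre-dose spirometry and before the first dose. No methacholine or bronchodilator is listed. Medication washouts are confirmed at this visit, and the section 4.1 washout table includes 6 hours for short-acting beta-agonists.

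**Visit 4 (section 6.2.4).** FeNO and spirometry are followed by "Perform Methacholine Challenge --- reschedule visit if FEV1 is < 60% or 1.5L", then the bronchodilator, the recovery challenge, and only then the blood draw.

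**Visit 5 (sections 6.2.4 and 6.2.5).** The order is the same, with the blood item worded "Collect Blood for cytokines, biomarkers and eosinophil count".

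**Narratives (Précis and section 3).** For both follow-up visits the sentence "10ml of blood will be collected for measurement of cytokines, biomarkers and blood eosinophil count" comes after the one on methacholine testing. These narratives mention no bronchodilator or recovery step at Visits 4 and 5.

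**Albuterol (section 6.2).** "Albuterol will be administered by inhalation (4 puffs) at the end of the methacholine provocation test".

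**Endpoints (sections 9.1 and 9.5.2).** The blood-marker outcomes are percentage decreases: 32% for eosinophils in subjects above 300 cells/ul, 40% for IL4, 50% for IL5 and 75% for IL13. Section 9.1 adds: "The same measurements of pulmonary function and inflammation status will be repeated at 28 and 56 days of ginger or placebo consumption". Section 9.6 gives no analysis for eosinophils or cytokines.

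**The concern.** A change from baseline isolates time and treatment only if both samples are taken under like conditions. Read down the page, the plan takes the baseline sample on a day with no challenge and after a confirmed beta-agonist washout, and takes each follow-up sample after induced bronchoconstriction and a bronchodilator. Any acute effect of either on circulating eosinophils or cytokines would be counted as change over treatment. It could not be separated afterwards, because no follow-up sample is specified as pre-challenge.

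What is at stake is the reading of the secondary blood markers, above all any responder proportion or mean change reported within one arm. The primary outcomes are not touched: in the 6.2.4 and 6.2.5 lists FeNO precedes the challenge, and PD20 is the challenge itself.

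**Working it through.** The plan states no figure on this point, so there is none to reproduce. The check has two parts.

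**1. Listed order, side by side**

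| Step | Visit 3 | Visits 4 and 5 |
|---|---|---|
| FeNO | before draw | before draw |
| Spirometry | before draw | before draw |
| Methacholine challenge | not done | before draw |
| Bronchodilator and recovery | not done | before draw |
| Study drug dosing | after draw | after draw |

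The challenge row of the section 6.1 schedule marks Visits 2, 4 and 5, not Visit 3. (Sections 9.1 and 9.5.1 call Visit 3 the baseline for PD20; the schedule, the visit lists and section 3 all put the baseline challenge at Visit 2, and I rely on those.) Section 3 puts Visit 3 one to two days after Visit 2, so baseline blood is not remote from a challenge, but none is given that day. No section places the follow-up draw before the challenge. The draws concerned number at most 36 × 2 = 72, or 32 × 2 = 64 with the 16 per arm expected after attrition.

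**2. What an acute shift would do**

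The documents give no size for a shift, so s below is an assumption, in SDs of the change score, with no drug effect on the marker and two-sided 0.05. The paired test is also an assumption for these markers: it is the within-patient test that section 9.6 names for FeNO.

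*Paired test in one arm:* noncentral t, n − 1 df, noncentrality s√n. For n = 16 and s = 0.5 this is 0.5 × 4 = 2.0.

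*Two-sample test of change:* 2n − 2 df, noncentrality f·s·√(n/2), where f is the difference in shift between arms as a fraction of s. If f = 0 the noncentrality is 0 and the rate is 0.05 for every s. For n = 16, s = 0.5 and f = 0.25 it is 0.25 × 0.5 × √8 = 0.354.

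False-positive rates, n = 16 (n = 18):

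| s | Paired, one arm | Between arms, f = 0 | Between arms, f = 0.25 |
|---|---|---|---|
| 0.25 | 0.155 (0.170) | 0.05 | 0.053 (0.054) |
| 0.5 | 0.465 (0.516) | 0.05 | 0.064 (0.065) |
| 1.0 | 0.962 (0.979) | 0.05 | 0.105 (0.113) |

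*How large could f be?* The challenge is titrated by doubling doses to a 20% FEV1 fall. The plan's success criterion of 0.7 doubling doses means 2^0.7 = 1.62 times the provoking dose. If the shift came wholly from methacholine and were strictly proportional to dose, f = 0.62, and the between-arm rates at n = 16 would be 0.071, 0.137 and 0.401 for the three values of s. That is an extreme case, since every patient stops at the same FEV1 fall.

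*Eosinophil responders with no drug effect:* P = Φ[(ln 0.68 − ln(1 + h))/σ], where h is the acute proportional shift and σ the SD of log change, both assumed.

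| σ | h = 0 | h = −10% | h = +10% |
|---|---|---|---|
| 0.2 | 2.7% | 8.1% | 0.8% |
| 0.3 | 9.9% | 17.5% | 5.4% |
| 0.4 | 16.7% | 24.2% | 11.5% |

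With a common shift the same proportion applies in both arms.

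**The case against.** **List order need not be the order of execution.** The Visit 3 to 5 lists are headed "Procedures Performed"; only the Visit 1 list is headed "Sequence of events". The lists are not strictly chronological: Visit 3 puts the one-hour post-dose spirometry above the 0.5-hour PK draw. The schedule places FeNO below the recovery challenge, whereas the lists place it above. This stands, so one can say that the draw is listed after the challenge, not that it is known to be taken after it. It does not remove the need for a change: if the order is open, timing may vary between subjects and visits, and the same edit settles it.

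**No acute effect is documented.** Also correct. A reader might infer that the secondary endpoints are confounded, or that every follow-up sample is taken minutes after provocation and four puffs of albuterol. The documents support neither. They report no effect of methacholine or albuterol on these markers and give no interval between challenge and draw. They also disagree on albuterol: section 6.2 has it given at the end of the challenge, while sections 5.1, 7 and 7.1 describe it as available if the participant is uncomfortable. Those passages must be reconciled.

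**Randomization protects the comparison.** Both arms follow the same visit procedures, so a common shift cancels between arms. This stands, and it limits the point mainly to within-arm readings. It is not a full answer, because the endpoints are written as within-subject percentage falls and no between-arm analysis of them is specified.

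**Section 9.1 promises the same measurements, not the same conditions.** Agreed; this is not a contradiction in the plan.

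**The PK profiles share the listed order.** True, but the stated PK aim is to establish parameters, with no change-from-baseline test, so no harm is shown.

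**Conclusion.** The point holds as a conditional one. In the procedure lists, and in the narratives as far as they go, the follow-up draw comes after the methacholine challenge, while the baseline draw has no challenge or bronchodilator that day. If that order is followed, any acute effect would be mixed into the within-subject changes in eosinophils and cytokines.

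The size cannot be known from the documents. Under assumed shifts of 0.25 to 1.0 SD, a within-arm paired test with 16 patients has a false-positive rate of 0.155 to 0.962, while a between-arm test stays at 0.05 if the shift is common. A between-arm bias is second-order: it needs an acute effect, dependence of that effect on the methacholine dose received, and a ginger effect on PD20. Even then it is smaller than the within-arm error at every shift examined.

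Only secondary endpoints of a pilot trial are affected. Severity is minor to moderate; the case for acting is that the remedy is cheap.

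**What to change.** In the Visit 4 and 5 lists (6.2.4 and 6.2.5), move the cytokine, biomarker and eosinophil draw to directly after FeNO and spirometry and before the methacholine challenge, matching Visit 3. Reorder the Visit 4 and 5 narratives in the Précis and section 3 to agree, and state that this order is the order of execution.

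Cost: one existing line is moved at each visit, with no added procedure or blood volume. In the eight PK subjects this draw may have to be taken separately from the pre-dose PK sample.

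It would also help to specify in section 9.6 a between-arm analysis of these markers, for example ANCOVA on log values with baseline as covariate, so that a shift common to both arms cannot be read as a ginger effect.
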